# 2.2. Background

Nonalcoholic Steatohepatitis

Nonalcoholic steatohepatitis (NASH) is the progressive stage of nonalcoholic fatty liver disease (NAFLD), characterized histologically by the presence of steatosis, lobular inflammation, and hepatocyte injury (ballooning), with or without fibrosis (Chalasani et al. 2018). Noncirrhotic NASH is a silent disease with few clinical symptoms and requires a liver biopsy for diagnosis. As a consequence, the prevalence of NASH in the general population is unclear, but estimated to be between 1.5% and 6.45% (Younossi et al. 2016). Obesity, T2DM, and dyslipidemia are considered important risk factors for NAFLD (Chalasani et al. 2018). The risk of NASH is ~2-fold higher for patients with diabetes versus patients who do not have diabetes (Williams et al. 2011; Loomba et al. 2012). The prevalence of NASH in patients with morbid obesity has been reported to be 37% (Machado et al. 2006). Those with NASH, especially in the presence of fibrosis, are at a higher risk for adverse outcomes, including liver cirrhosis, liver-related mortality, and cardiovascular mortality (Angulo et al. 2015). NASH is currently the third-most common cause of hepatocellular carcinoma (Van Thiel and Ramadori 2011; Chalasani et al. 2018). Due to its increasing prevalence, NASH is expected to become the most common indication for liver transplantation in forthcoming years overtaking viral hepatitis (Charlton et al. 2011).

There are currently no approved pharmacological therapies available for treatment of NASH. The beneficial effects of weight loss on NASH are well-documented (Promrat et al. 2010; Vilar-Gomez et al. 2015; Chalasani et al. 2018); therefore, currently diet and exercise are considered the standard treatment for NASH. For example, losing  $\geq 5\%$  body weight was shown to improve hepatic steatosis, induce resolution of NASH, and stabilize or improve fibrosis. A  $\geq 10\%$  body weight decrease is associated with improvements in all features of NASH, including fibrosis regression (Vilar-Gomez et al. 2015; Chalasani et al. 2018). The relationship between NASH, increased body weight, and T2DM provides a strong rationale to investigate therapies that induce weight loss and improve insulin sensitivity.

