- ii. CAP >288 dB/m by TE, or higher at the discretion of the investigator
- iii. LSM >7.6 kPa and < 20 kPa by TE
- iv. AST >23 U/L
- v. FibroScan-AST (FAST) score >0.35 (see Section 8.1.3.3.1 for details)

When TE is of insufficient quality (See definitions in Section 8.1.3.3) or LSM is >7.1 but  $\le 7.6$  kPa and/or the CAP is >283 but  $\le 288$  dB/m, following criteria may be used:

- i. T2DM or at least 2 weight-related comorbidities (as defined above)
- ii. Fibrosis -4 (FIB-4) >1.3 and <3.2
- iii. AST >23 U/L
- 6. NAFLD Activity Score (NAS)  $\geq 4$  with  $\geq 1$  point for each component
- 7. Fibrosis stage 2 or 3 according to the NASH CRN scoring system
- 8. Stable body weight (≤5% body weight change) for at least 3 months. For participants entering the study with a liver biopsy done between 3 to 6 months from the screening visit, body weight must be stable (<5% body weight change) for the period of time between the biopsy and the screening visit.
- 9. Participants currently treated with vitamin E (≥400 IU QD) or TZDs for NASH need to remain on treatment during the study, and need to be on a stable dose for at least 6 months prior to screening or need to be off treatment for at least 6 months prior to screening
- 10. Participants with a documented history of Gilbert's syndrome may be enrolled if the direct bilirubin is within normal reference range
- 11. Individuals who are, in the investigator's opinion, well-motivated, capable, and willing to:
  - a. Self-inject study drug or have the assistance of a trained individual who will inject the study drug
  - b. Undergo baseline and endpoint liver biopsies

c. Maintain a study diary, as required for this protocol

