### 9. Statistical Considerations

# 9.1. Statistical Hypotheses

The primary hypothesis that is being tested in this study is that tirzepatide 5 mg, 10 mg or 15 mg administered SC QW is superior to placebo with regards to resolution of NASH with no worsening of fibrosis at week 52.

Major secondary hypotheses are that tirzepatide is superior to placebo with regards to

- Regression of fibrosis with no worsening of NASH at Week 52.
- Prevention of fibrosis progression at Week 52.
- Decrease of NAS by ≥2 points at Week 52.
- Absolute decrease in liver fat content by MRI-PDFF at Week 52.
- Decrease in body weight at Week 52.

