### 9.4.7. Subgroup Analyses

Subgroup analyses of important factors, including fibrosis stage, amount of weight loss, baseline BMI, baseline liver fat content, T2DM status, and other factors to be specified in the SAP are planned for the key outcomes. The models used for these analyses will vary depending on the subgroups and the outcome. More details of the modeling will be provided in the SAP. Other exploratory subgroup analyses may be performed as deemed appropriate.

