- Population: participants who meet the inclusion criteria. Further details can be found in Section 5 of Protocol GPHR.
- Endpoint: NASH resolution without worsening of fibrosis at 52 weeks.
- Treatment condition: the randomized treatment.
- The ICE “permanent discontinuation of study drug” is handled by the hypothetical strategy and the potential outcome of interest is the response in the efficacy measurement if participants had adhered to the randomized treatment. There are no other defined ICES.
- Population-level summary: proportion of patients meet NASH resolution without worsening of fibrosis at Week 52.

Treatment effect of interest is thus defined as the difference in proportion of NASH resolution without worsening of fibrosis at Week 52 between QW LY3298176 (tirzepatide) and placebo. Rationale for “efficacy estimand”: This Phase 2 study aims to study the efficacy of LY3298176 (tirzepatide) under the ideal condition that all participants adhere to the randomized treatment. Data collected after the ICE will be set to missing.

Estimand(s) for Secondary Objectives

The same estimand for the primary objective will be used for the secondary efficacy endpoints for the secondary objectives.

Treatment-regimen estimand

The second estimand, the “treatment-regimen” estimand, represents the efficacy irrespective of adherence to investigational product and availability of the postbaseline biopsy. There are no ICE.

Unless specified otherwise, safety analyses will be conducted using the SS.

The end of study participation for a patient will be the earliest of date of death, date of withdrawal from further participation in the study, or date of the safety follow-up visit (Visit 801). For patients considered to be lost to follow-up, end of study participation will be the date of lost to follow-up reported by the investigator. Patient data included in the database after the last date of study participation (date of death, date of early termination or date of safety follow-up) will be excluded from statistical analyses. A listing of such data may be provided.

Summary statistics for categorical measures (including categorized continuous measures) will include sample size, frequency, and percentages. Summary statistics for continuous measures will include sample size, mean, SD, median, minimum, and maximum. The summary statistics

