3.15. Subgroup Analyses

Efficacy subgroup analyses will be guided by the efficacy estimand. Subgroups with few subjects may be excluded from subgroup analyses when appropriate. Subgroup analyses will include, but are not limited to:

- Primary and secondary endpoints by baseline T2DM status.
- Primary endpoint by baseline NAS score, using median NAS score to divide into 2 subgroups. In the case that baseline NAS score median is 4, NAS score 4, and NAS score greater than 4 will be the 2 subgroups.
- Primary endpoint by baseline liver fat (MRI-PDFF) category, using median to divide into 2 subgroups.
- Primary endpoint by baseline cT1 category, using median to divide into 2 subgroups.
- Primary endpoint by baseline serum NASH biomarkers (ALT, K-18, NIS4), using median (or cutoffs based on literature) to divide into 2 subgroups for each biomarker.
- Primary endpoint by categories of weight loss, using <5% and ≥5% as categories and then <10% and ≥10% as categories.
- Secondary endpoints of fibrosis regression and fibrosis progression by baseline fibrosis stage category (2 versus 3).
- Secondary endpoint of decreasing NAS by ≥2 points by baseline NAS.

- Secondary endpoints of fibrosis regression and fibrosis progression by baseline categories of serum fibrosis biomarkers (ELF and Pro-C3). For ELF, subgroups <9.8 and ≥ 9.8 (threshold for advanced fibrosis) will be analyzed (EASL 2021). For Pro-C3, subgroups <13.4 versus ≥ 13.4 and <20.2 versus ≥ 20.2 ng/ml (Nielsen et al. 2021) will be analyzed. If these subgroups for ELF and Pro-C3 are very imbalanced, the medians will be used to create the subgroups.

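### The primary endpoint is to be analysed by on-study weight-loss category as if it were a baseline subgroup; arm contrasts within those categories are not randomised comparisons and can be biased.

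*SAP*

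**What the plan says.** SAP 3.15 includes this item in its subgroup list: "Primary endpoint by categories of weight loss, using <5% and ≥5% as categories and then <10% and ≥10% as categories". Every other factor in that list (T2DM status, NAS, liver fat, cT1, serum biomarkers, fibrosis stage) is labelled as baseline. The section opens with "Efficacy subgroup analyses will be guided by the efficacy estimand". SAP 3.2 defines what that estimand targets: "Treatment effect of interest is thus defined as the difference in proportion of NASH resolution without worsening of fibrosis at Week 52", between tirzepatide and placebo. It adds that statistical treatment comparisons are made between the tirzepatide doses and placebo.

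Protocol 9.4.7 is the source of the item: "Subgroup analyses of important factors, including fibrosis stage, amount of weight loss, baseline BMI, baseline liver fat content, T2DM status". Amount of weight loss and baseline BMI appear there as separate factors. Protocol 9.4.7 leaves the modelling details to the SAP, and SAP 3.15 gives none for this item. It does not say at which visit weight loss is taken, or whether the table is descriptive or inferential.

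**The concern.** Three statements in the protocol show what kind of variable this is.

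- Entry criterion 8 (Protocol 5.1) requires "Stable body weight (≤5% body weight change) for at least 3 months", so the 5% and 10% categories can only describe change during the study.
- Protocol 9.1 makes "Decrease in body weight at Week 52" a secondary hypothesis, so the arms are expected to differ on it.
- Protocol 2.2 reports that losing at least 5% "body weight was shown to improve hepatic steatosis, induce resolution of NASH, and stabilize or improve fibrosis", so it is tied to the primary endpoint.

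A subgroup factor fixed before randomisation leaves the arms comparable within each level. A factor that treatment changes does not. A placebo participant who loses 10% is unusual for that arm, and a 15 mg participant who loses less than 5% is unusual the other way. If whatever makes them unusual also affects histology, the within-category contrast mixes that selection with the drug effect. Diet adherence is an obvious candidate, because all arms receive counselling.

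The table would naturally be read as showing whether the liver effect depends on weight loss. The study's data are meant to support Phase 3 dose selection (Protocol 2.1). A within-category contrast cannot answer that question without assumptions that the SAP does not state.

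**Working it through.** **1. The plan's own denominator.** SAP 2.2 gives 196 randomised 1:1:1:1 with 20% dropout: 196 × 0.8 / 4 = 39.2, which the plan rounds to about 40 completers per arm. I use 39.

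**2. Expected cell sizes.** Protocol 2.2 gives Week 26 shares from the earlier T2DM study for 5, 10 and 15 mg: 50.0%, 77.3% and 85.7% losing at least 5%, and 16.8%, 45.5% and 54.3% losing at least 10%. The documents give no placebo share, so I assume placebo loss is normal with mean 1% and SD 6.

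- 15 mg, below 5%: 39 × (1 − 0.857) = 5.6
- Placebo, at or above 10%: 39 × P(Z ≥ (10 − 1)/6) = 39 × 0.0668 = 2.6
- Placebo, at or above 5%: 39 × P(Z ≥ (5 − 1)/6) = 39 × 0.2525 = 9.8
- 5 mg, either side of 5%: 39 × 0.50 = 19.5
- 10 mg, at or above 10%: 39 × 0.455 = 17.7

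Some cells are small and others are not.

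**3. Bias when the drug does nothing to histology.** Let U be a standard normal factor shared by weight loss and resolution.

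- Weight loss = m + 6 × (rU + √(1 − r²) × e), with e an independent standard normal. For placebo, m = 1. For 15 mg, m = 5 + 6 × Φ⁻¹(0.857) = 5 + 6 × 1.067 = 11.4, which reproduces the 85.7% share.
- Logit P(resolution) = a + bU in both arms, with a set so that 12.3% resolve overall. Using the plan's 12.5% leaves the odds ratios unchanged to two decimals.

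The true odds ratio is 1, so any departure from 1 is bias. Odds ratios for 15 mg versus placebo, by numerical integration:

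| r | b (log-odds per SD) | <5% | ≥5% | <10% | ≥10% |
|---|---|---|---|---|---|
| 0 | 1 | 1.00 | 1.00 | 1.00 | 1.00 |
| 0.2 | 0.5 | 0.89 | 0.91 | 0.92 | 0.88 |
| 0.5 | 1 | 0.57 | 0.66 | 0.66 | 0.57 |
| 0.67 | 1 | 0.45 | 0.57 | 0.56 | 0.47 |

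Simulation of the same model agrees to within about 0.01 (0.56 to 0.66 in the third row). One cell worked through, r = 0.5 at ≥10%: resolution is 15.3% on 15 mg and 24.0% on placebo, so the odds ratio is (0.153/0.847) / (0.240/0.760) = 0.57.

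**4. Bias when the drug works.** A differently built model gives the same direction. It uses the plan's 42.5% against 12.5% (a difference of 0.30), an assumed placebo share of 5% or 15% above the 5% cut, and a loading of 0.5 for both weight loss and response on a shared factor. For 15 mg, the ≥5% category shows a difference of 0.19 to 0.23, against a true 0.31 in those treated patients. The <5% category shows 0.16 to 0.17 against 0.22. With a loading of zero both categories return 0.30.

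**The case against.** **The bullet orders no test.** It names no model, interaction term or within-category contrast, and a table of response by category and arm would satisfy it. A reader might infer that the SAP explicitly prescribes a between-arm test in each category; it does not. But the item sits among the efficacy subgroups, the section is governed by an estimand that is an arm difference, SAP 3.2 makes comparisons against placebo, and nothing marks this item as descriptive. Followed as written, the plan leads to arm contrasts.

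**The bias is conditional.** This stands. With no shared cause other than treatment there is none, as the first row of the table shows. The SAP neither states nor defends that assumption.

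**The inputs are assumed.** This also stands. The values of r and b, and the placebo distribution, are not in the documents. The 85.7% is a Week 26 rate in T2DM participants, applied to a 52-week study in which 35% to 60% have no T2DM. The common SD of 6 implies 59% of 15 mg participants at or above 10%, against 54.3% in the earlier study. The null scenario also lets weight loss itself have no effect on resolution, contrary to Protocol 2.2. The figures are a range for illustration, not a prediction.

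**Small subgroups may be dropped, and the study is exploratory.** SAP 3.15 allows subgroups with few subjects to be excluded. That deals with imprecision but not with selection. SAP 3.6 calls this an exploratory Phase 2 study without multiplicity adjustment. That limits the consequence but does not make the contrast interpretable.

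**Conclusion.** The point holds. On-study weight loss is affected by treatment, and contrasts between arms within its categories are not randomised comparisons. They are biased to the extent that weight loss and histology share causes other than treatment. Under the assumed inputs, the within-category odds ratio for 15 mg with no true effect runs from 1.0 (no shared cause) through 0.88 to 0.92 and about 0.57 to 0.66, down to 0.45 to 0.57 at the strongest setting.

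Four stronger readings are not supported.

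- The bias is not certain, and its size cannot be derived from the documents.
- A reader might infer that the table could also create a false benefit. Every scenario examined with a shared cause runs against tirzepatide.
- The cells are not nearly empty throughout. Placebo at or above 5% is about 10 of 39 under the same assumption.
- The primary analysis, its error rate and the sample size are untouched. This concerns how one exploratory table is specified and read.

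**What to change.** In SAP 3.15, take weight loss out of the treatment-effect subgroups. Replace it with a descriptive table of NASH resolution without worsening of fibrosis by weight-loss category within each arm. State the time point of the weight loss (for example Week 52), and give no tirzepatide-versus-placebo test or estimate within category. Keep baseline BMI, named in Protocol 9.4.7 but not in the SAP's list, as the true weight-related subgroup. Protocol 9.4.1 allows analysis changes that do not alter a principal feature to be described and justified in the SAP, so a protocol amendment should not be needed for this.

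A mediation analysis is optional and not part of this fix. With about 40 completers per arm it would be imprecise, and it would need its own stated assumptions.

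The cost is a few lines of SAP text and one table shell. The small downside is that a familiar subgroup table becomes descriptive.

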3.16. Important Protocol Violations

Important protocol deviations are identified in the Trial Issues Management Plan. A listing and a summary of important protocol deviations by treatment will be provided.

3.17. Interim Analyses and Data Monitoring

There will be a futility interim analysis based on relative liver fat reduction based on MRI-PDFF measurements. It will be done based on data from approximately 80 participants being on study treatment for 26 weeks. An internal AC will be formed to review unblinded interim analysis.

Detailed information regarding futility analysis and safety reviews including the statistical reports to be reviewed by the AC will be described in the program AC Charter and a separate interim analysis SAP.

4. Unblinding Plan

Details of the blinding and unblinding will be provided in Blinding and Unblinding Plan document for Study GPHR.

5. Novel Coronavirus (COVID-19) Impact

This section lists the potential statistical analyses that may be performed to assess the impact of COVID-19 pandemic when appropriate.

5.1. General Consideration

Percentage and count of randomized participants who followed the COVID-19 mitigation plan may be summarized by treatment group. This includes, but not limited to, participants rescreened, procedures conducted via remote visit or mobile home health visit, visits occurred using the extended visit windows, alternative way of investigator product shipment/dispensing, use of a local laboratory, etc.

Percentage and count of randomized participants who completely missed at least 1 study visit due to COVID-19 pandemic may also be summarized.

5.2. Exposure

A listing of randomized participants who had study drug temporary interruption due to COVID-19 pandemic may be provided.

5.3. Protocol Deviation

Percentage and count of randomized participants having important protocol deviation related to COVID-19 pandemic may be summarized by treatment.

Percentage and count of randomized participants with protocol deviation related to COVID-19 pandemic may also be summarized by treatment.

A listing of all randomized participants who had important protocol deviation due to COVID-19 pandemic may be provided.

5.4. Patient Disposition

A summary table for all randomized participants that discontinue study or study treatment due to COVID-19 pandemic may be provided by treatment.

A listing of randomized participants who discontinued the study or study treatment due to COVID-19 infection may be provided.

5.5. Adverse Events

A listing of randomized participants who had COVID-19 infection, including death due to COVID-19, during the postrandomization period may be provided.

5.6. Local Laboratory

If local laboratory data was brought into the Lilly database, additional details around how to combine with central laboratory data and analyze it may be provided.

5.7. Missing Data Due to COVID-19

For the primary endpoints and key secondary endpoints, missing data due to COVID-19 may be handled as described in Section 3.11.1.3.

6. Supporting Documentation

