# 8.1. Efficacy Assessments

# 8.1.1. Primary Efficacy Assessment

The primary efficacy measurement in this study is NASH resolution with no worsening of fibrosis based on liver histology at Week 52 compared with baseline.

In alignment with United States (US) Food and Drug Administration (FDA) draft guidance (FDA 2018) and the EMA reflection paper (EMA 2018), NASH resolution will be defined as:

- absence of fatty liver disease or simple steatosis without steatohepatitis;
- the absence of hepatocellular ballooning (NAS 0 for ballooning)
- with or without mild lobular inflammation (NAS 0 or 1 for inflammation), and
- any value for steatosis.

No worsening of fibrosis will be defined as no increase in fibrosis stage from baseline to Week 52.

Liver histology will be evaluated via liver biopsies collected at baseline in participants for whom a liver biopsy of adequate quality performed within 6 months of screening is unavailable, and at Week 52 (end-of-treatment) in all participants who remained on study drug. Patients who discontinued study drug prior to Week 36 will not have a second liver biopsy.

Histology will be scored according to the NASH CRN guidelines (Kleiner et al. 2005; Puri and Sanyal 2012). Pathologists reviewing the liver biopsies will be blinded to treatment group. Intra- and inter-observer variability in assessment of histology will be assessed. The glass slides may be scanned to facilitate future additional exploratory analyses of the whole slide images.

Liver biopsy tissue block and slides will be retained at a facility selected by Lilly or its designee for a maximum of 15 years after the last participant visit for the study, or for a shorter period if local regulations and ERBs impose shorter time limits. This retention period enables use of new technologies, response to regulatory questions, and investigation of variable response that may not be observed until later in the development of tirzepatide or after tirzepatide becomes commercially available.

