3.4. Handling of Dropouts or Missing Data

For the analyses of primary and key secondary efficacy endpoints related to histology, data for participants with missing postbaseline liver biopsy will be excluded and not be imputed. A separate analysis for these endpoints may be conducted using FAS, where missing postbaseline biopsies will be imputed based on the method described in Section 3.11.1.3.

Unless specified otherwise, imputation of missing data for exploratory purposes will be limited to primary and key secondary efficacy endpoint analyses.

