3.11. Efficacy Analyses

The assessment of the primary, secondary and exploratory endpoints will be guided by the “efficacy” estimand. Analyses relative to the “efficacy” estimand will be conducted using the EAS without imputation of missing data. For exploratory purposes, and in the event of patients dropping out before Week 36, primary and key secondary efficacy analyses may be repeated using the EXAS guided by the “efficacy” estimand.

For informational purposes, the analysis of primary and key secondary endpoint may be repeated to be guided by the “treatment-regimen” estimand, which represents the efficacy irrespective of adherence to investigational product. Analyses relative to the “treatment-regimen” estimand will be conducted using the FAS. In this case, missing postbaseline measures will be imputed according to Section 3.11.1.3.

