3.11.1.3. Methods for Multiple Imputations

For efficacy analyses relative to “treatment-regimen” estimand, the ICEs and the resulting missing values will be handled as follows:

There are no ICE for “treatment-regimen” estimand. If the endpoint biopsy is not collected, data from participants who discontinue, but with non-missing endpoint biopsy from the same treatment arm will be used to impute the missing value (retrieved dropout imputation). In cases where there are not enough retrieved dropouts to provide a reliable imputation model, the imputation of missing data will be done with the jump-to-reference (placebo) imputation approach.

For NASH resolution with no worsening of fibrosis which is a binary endpoint and multiple conditions (see Section 3.11.1) need to be satisfied in addition to no increase in fibrosis score, the imputation will be done for each of the components separately. That is, ballooning score, steatosis score, inflammation score, and fibrosis score will be imputed separately. At the end, the imputed values will determine if the participant satisfies all criteria to have “Yes” for NASH resolution with no worsening of fibrosis or “No” otherwise based on the criteria listed in Section 3.11.1.

The statistical inference over multiple imputation of missing data is guided by methodology proposed by Rubin (1987).

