3.11.2.3. The Analysis Relative to the Treatment-Regimen Estimand

The analysis related to treatment-regimen estimand for all secondary outcomes may be conducted using the FAS. The same model described in Section 3.11.2.2 will be used for the analysis of binary outcomes. Missing values of the fibrosis score and components of NAS will be imputed according to Section 3.11.1.3.

For the mean body weight and mean absolute change in liver fat content by MRI-PDFF at Week 52, the analyses will be conducted utilizing ANCOVA described in Section 3.11.2.1. Imputation of missing data will be done with the jump-to-reference (placebo) imputation approach.

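### SAP 5.7 does not say which estimand its COVID-19 rule serves, and the imputation it points to has no branch for a participant still on study drug, so the optional treatment-regimen estimate can be pulled toward no difference

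*SAP*

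**What the plan says.** SAP 5.7 deals with pandemic-related gaps in the primary and key secondary endpoints in one sentence: "missing data due to COVID-19 may be handled as described in Section 3.11.1.3". It is permissive and names no estimand.

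SAP 3.11.1.3, the section it cites, is written for the treatment-regimen estimand. It is triggered whenever the endpoint biopsy was not collected, for any reason, and offers two models:

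- Retrieved dropout: "data from participants who discontinue, but with non-missing endpoint biopsy from the same treatment arm will be used to impute the missing value".
- Fallback, when there are too few such donors: "the imputation of missing data will be done with the jump-to-reference (placebo) imputation approach".

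For Week 52 body weight and MRI-PDFF in the treatment-regimen analysis, SAP 3.11.2.3 has one rule, again regardless of reason: "Imputation of missing data will be done with the jump-to-reference (placebo) imputation approach".

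The efficacy-estimand analysis, which is the primary one, works differently. SAP 3.4 states that "data for participants with missing postbaseline liver biopsy will be excluded and not be imputed", and SAP 3.11 states that these analyses "will be conducted using the EAS without imputation of missing data". The treatment-regimen analysis is optional: "For informational purposes, the analysis of primary and key secondary endpoint may be repeated".

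**The concern.** A participant who takes 52 weeks of study drug but whose biopsy is cancelled by a site closure has neither stopped treatment nor moved to placebo. Only the observation is lost. The definitions in SAP 3.2 agree: the sole intercurrent event of the efficacy estimand is permanent discontinuation of study drug, and the treatment-regimen estimand has none. Under either, the value wanted for this participant is the outcome on the assigned drug. SAP 3.11.1.3 and 3.11.2.3 cannot supply it, because they do not separate missing-on-drug from missing-off-drug.

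The situation is foreseeable. Protocol Appendix 10 limits remote visits to Visits 4 through 13 and follow-up, so the Visit 14 biopsy has no remote substitute.

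Two things are at stake. One is whether COVID-19 gaps in the primary endpoint are excluded or imputed, which the SAP leaves open. The other is whether the treatment-regimen analysis, the SAP's only imputation-based companion to an analysis that drops participants without biopsies, carries an avoidable bias.

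**Working it through.** **1. Which rule applies to an on-drug participant with no Week 52 result**

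| Analysis | Missing biopsy | Missing weight or MRI-PDFF |
|---|---|---|
| Efficacy estimand, EAS (SAP 3.4, 3.11, 3.11.2.1) | excluded, no imputation | MMRM, no imputation |
| Treatment-regimen estimand, FAS, optional (SAP 3.11.1.3, 3.11.2.3) | same-arm discontinuers, else placebo | placebo |
| COVID-19 (SAP 5.7), optional | 3.11.1.3; estimand not stated | 3.11.1.3; estimand not stated |

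The last row agrees with the second only if 5.7 is confined to the treatment-regimen analysis. Applied to the primary analysis, it contradicts the first.

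**2. The plan's own figure**

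Inputs (SAP 2.2): response 42.5% on tirzepatide and 12.5% on placebo, two-sided 0.05, at least 80% power, 20% dropout, 1:1:1:1, 196 randomized, about 40 completers per arm.

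- The two-proportion formula gives 34 per arm, or 40 with continuity correction.
- 40/(1 − 0.20) = 50 per arm, or 200 in total, against 196 stated.
- 196 × 0.8/4 = 39.2 completers per arm.
- Power at 39 to 40 per arm is 0.857 to 0.866 (pooled z) or 0.808 to 0.821 (Fisher exact).

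The planning figures reproduce, so they are a fair base.

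**3. Placebo fallback, on-drug gaps only**

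Let m be the share of a tirzepatide arm that is on drug with no biopsy, and r the composite response rate at which it is imputed. SAP 3.11.1.3 imputes the histology components separately; r stands for the net result.

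Expected difference = (1 − m) × 0.425 + m × r − 0.125

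With r = 0.125 this is 0.30 × (1 − m), a loss of 0.3 point per 1% missing. The documents give no value for m, so a range is shown.

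| m (assumed) | Difference, points | Odds ratio |
|---|---|---|
| 0% | 30.0 | 5.17 |
| 2% | 29.4 | 5.05 |
| 5% | 28.5 | 4.86 |
| 10% | 27.0 | 4.57 |
| 20% | 24.0 | 4.02 |

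Equal missingness in the placebo arm does not offset this: placebo participants imputed as placebo keep their expected rate. For weight and MRI-PDFF the mean difference shrinks by the same factor (1 − m); the documents give no planning effect for these.

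**4. Retrieved-dropout branch at m = 10%**

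The donors' response rate is not in the documents. The difference is 27.0 points if it is 12.5%, 28.25 if 25%, 28.75 if 30%, and 30.0 (no dilution) if 42.5%.

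**5. Which branch is likely**

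Protocol 8.1.1: "Patients who discontinued study drug prior to Week 36 will not have a second liver biopsy". Protocol 8.1.1.3 makes the biopsy possible, not mandatory, for those who stop after at least 36 weeks on treatment, within 2 weeks of stopping. With 20% dropout, about 10 of 49 per arm stop, and only late stoppers with a biopsy can be donors. The placebo fallback is therefore the likelier branch.

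**6. With 20% dropout as well**

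If dropouts are also imputed as placebo, the expected difference under the present fallback is 0.30 × (0.80 − m): 22.5 points at 5%, 21.0 at 10%, 18.0 at 20%. If on-drug gaps are instead imputed from on-drug participants, it is 0.30 × 0.80 = 24.0 points whatever m is.

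Simulated power (49 per arm, 10 dropouts per arm, the same number of on-drug gaps in each arm, 50 imputations, Rubin's rules on the risk difference, no covariates, 20,000 runs):

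| On-drug missing per arm | Present fallback | On-drug branch added | Exclusion (primary rule) |
|---|---|---|---|
| 2 of 49 | 0.75 | 0.78 | 0.85 |
| 5 of 49 | 0.66 | 0.75 | 0.83 |
| 10 of 49 | 0.50 | 0.69 | 0.75 |

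Under exclusion the expected difference stays at 30.0 points if the missingness is unrelated to outcome. Only precision is lost, from a power of 0.87 with dropout alone.

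**The case against.** The strongest reply is that the result that matters is not touched. The primary histology analysis excludes missing biopsies. Weight and MRI-PDFF are analysed by MMRM on the EAS, which already treats a missing Week 52 value as missing at random given the participant's other data. The imputation rules belong to an optional, informational analysis, and 5.7 itself is permissive. All of this stands. A reader might infer that the headline tirzepatide effect is diluted; SAP 3.4 and 3.11 do not support that. What remains is that 5.7 refers to the primary endpoint and does not say that those sections still govern it.

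Further replies:

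- *Donors are not poor responders by definition.* They have at least 36 weeks of exposure and a biopsy near the last dose. This stands: dilution through that branch is possible but not established.
- *SAP 3.11.2.3 is not a COVID-19 rule.* Correct: 5.7 cites 3.11.1.3 only. But 3.11.2.3 still covers a scan or weight missed for any reason in the treatment-regimen analysis.
- *The size is modest.* At 40 per arm the standard error of the difference is √[(0.425 × 0.575 + 0.125 × 0.875)/40] = 9.4 points, against 1.5 to 3.0 points lost at 5% to 10%. Protocol Appendix 10 also allows flexible Visit 14 timing and extra study drug, which should limit the gaps. Both are fair, but the loss is systematic and avoidable.
- *Reference-based imputation is a recognised conservative choice.* It is, for participants who stopped drug. That reason does not extend to those who did not.

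A reader might also infer that the comparison between doses is distorted. That would need administrative missingness to differ by dose. Assignment is randomized, blinded and stratified by region, and the documents give no reason for closures to cluster in one dose.

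**Conclusion.** The point holds in a limited form. SAP 5.7 is ambiguous about its estimand and, read literally, conflicts with 3.4 and 3.11. Where 3.11.1.3 and 3.11.2.3 are applied, a participant still on drug is modelled as a discontinuer or as placebo, which fits neither estimand in SAP 3.2.

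Under the placebo fallback the treatment-regimen estimate is biased toward no difference by 0.3 point per 1% of a tirzepatide arm affected: 1.5 points at 5% and 3.0 at 10%, from 30.0. This rests on the planning rates, on assumed shares, and on the missing on-drug participants responding like other on-drug participants. Under the retrieved-dropout branch, whether there is dilution, and how much, cannot be settled from the documents. The primary EAS estimate is not affected unless 5.7 is taken to override 3.4 and 3.11.

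**What to change.** 1. In SAP 5.7, state that the reference to 3.11.1.3 applies only to the treatment-regimen analysis, and that the efficacy-estimand analysis follows 3.4 and 3.11 for COVID-19 gaps too.
2. In SAP 3.11.1.3 and 3.11.2.3, split missing Week 52 values by study-drug status:
   - Still on study drug, missing for an administrative reason such as COVID-19: impute under a stated MAR assumption from same-arm, on-drug participants with data. Keep the covariate set small given about 40 completers per arm, for example T2DM status, region, the baseline value and available Week 26 data.
   - Off study drug: keep the retrieved-dropout or jump-to-reference method as now specified.
3. List what counts as administrative. A participant who declines the biopsy is not clearly missing at random and should not enter the new branch by default.

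The cost is SAP wording, one more imputation branch and an explicit MAR assumption that the data cannot verify. No new data collection is needed.
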